10.0 DATA SUBMISSION SCHEDULE

Case report forms with appropriate source documentation will be completed according to the schedule listed in this section. Data may be up to 1 cycle behind at any given time.

| Case Report Form | Submission Schedule |
|--|---|
| Original Consent Form | Prior to registration |
| On-Study Form Medical History Form Treatment Assignment Form | Prior to starting treatment |
| ctDNA Form | Baseline, C3D1, C6D1, C9D1, C12D1, end of treatment |
| Treatment Form | Every cycle |
| Toxicity Form | Continuous |
| Treatment Summary Form | Completion of treatment |
| Follow Up Form | Frequency per study calendar |
| Imaging Form | Baseline, every 12 weeks for the first 2 years after surgery, every 24 weeks for the third year after surgery |
| Recurrence Form | Time of disease recurrence |
| Death Form | Time of death |
| MedWatch Form | See Section 7.0 for reporting requirements |

Any queries generated by Washington University must be responded to within 28 days of receipt by the participating site. The Washington University research team will conduct a regular review of data status at all secondary sites, with appropriate corrective action to be requested as needed.

10.1 Adverse Event Collection in the Case Report Forms

All adverse events that occur beginning with start of treatment (minus exceptions defined in Section 7.0) must be captured in the Toxicity Form. Baseline AEs should be captured on the Medical History Form.

Participant death due to disease progression should be reported on the Toxicity Form as grade 5 disease progression. If death is due to an AE (e.g. cardiac disorders: cardiac arrest), report as a grade 5 event under that AE. Participant death must also be recorded on the Death Form.

11.0 MEASUREMENT OF EFFECT

Tumor imaging is strongly preferred to be acquired by CT. For the abdomen and pelvis, contrast-enhanced MRI may be used when CT with iodinated contrast is contraindicated, or when mandated by local practice. The same imaging technique regarding modality, ideally the same scanner, and the use of contrast should be used in a participant throughout the study to optimize the reproducibility of the assessment of existing and new tumor burden and improve the accuracy of the assessment of response or progression based on imaging.

For the purposes of this study, patients should be re-evaluated every 12 weeks (+/- 2 weeks) for the first two years then every 24 weeks (+/- 2weeks) x2 for the third year, in addition to a baseline scan.

Relapse-free survival is defined as the time from randomization to any of the following events:

recurrence of melanoma at any site (local, in-transit or regional lymph nodes or distant recurrence) or death due to any cause. New incident cases of melanoma and second cancer diagnoses are not counted as events for recurrence-free survival.

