5.6 Duration of Therapy

If at any time the constraints of this protocol are considered to be detrimental to the patient's health and/or the patient no longer wishes to continue protocol therapy, the protocol therapy should be discontinued and the reason(s) for discontinuation documented in the case report forms.

In the absence of treatment delays due to adverse events, treatment may continue for up to 13 cycles or until one of the following criteria applies:

- Documented and confirmed disease progression
- Death
- Adverse event(s) that, in the judgment of the investigator, may cause severe or permanent harm or which rule out continuation of study drug
- General or specific changes in the patient's condition render the patient unable to receive further treatment in the judgment of the investigator
- Suspected pregnancy
- Serious noncompliance with the study protocol
- Lost to follow-up
- Patient withdraws consent

- Investigator removes the patient from study
- The Siteman Cancer Center decides to close the study

Patients who prematurely discontinue treatment for any reason will still be followed as indicated in the study calendar with the exception of discontinuation due to disease recurrence; patients who stop treatment due to recurrence will be considered off study and will no longer be followed after the 90-day follow-up for adverse events is completed.

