5.7 Duration of Follow-up

Follow-up frequency is calculated from date of surgery. After surgery, patients will be followed every 12 weeks for 2 years and every 24 weeks for 1 additional year. Frequency and duration of follow-up after the end of treatment depends on when treatment is discontinued. Patients will be followed for 3 years from date of surgery regardless of when treatment is discontinued unless treatment is discontinued due to disease recurrence, in which case the patient will be considered off study after the 90-day follow-up for adverse events is completed. Patients removed from study for unacceptable adverse events will be followed until resolution or stabilization of the adverse event.

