 - Grade 4 lymphopenia or leukopenia ≤ 14 days in duration.
 - Isolated Grade 4 amylase or lipase abnormalities that are not associated with symptoms or clinical manifestations of pancreatitis and decrease to Grade < 4 or return to baseline within 7 days.
 - Isolated Grade 4 electrolyte imbalances/abnormalities that are not associated with clinical sequelae and are corrected with supplementation/appropriate management within 72 hours of their onset.
 - Grade 4 treatment -related endocrinopathy AEs (except adrenal insufficiency or hypophysitis), such as hyper- or hypothyroidism, or glucose intolerance, which resolve or are adequately controlled with physiologic hormone replacement (corticosteroids at ≤ 10 mg of prednisone or equivalent per day, thyroid hormones) or glucose-controlling agents,

respectively, may not require discontinuation after discussion with and approval from the Medical Monitor.

- Any AE, laboratory abnormality, or intercurrent illness that, in the judgment of the Investigator, presents a substantial clinical risk to the patient with continued treatment.
- Disease recurrence (local, regional, or distant), including new primary melanoma (except MMIS Stage 0) Note: Non-melanoma skin cancer does not require treatment discontinuation. In the absence of intolerable toxicity, patients with diagnosed MMIS Stage 0 melanoma will be eligible to continue study treatment using the same dose and schedule for their original melanoma of up to approximately 1 year of study treatment starting from first dose, at the discretion of the Investigator.

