14.3 Secondary Endpoints

- Confirmed ctDNA negative rate, defined as the proportion of ctDNA-positive patients having two consecutive negative ctDNA tests.
- Relapse free survival (RFS), defined as the duration of time from the date of positive ctDNA being confirmed to the date of earliest disease relapse or death, whichever occurs first. Patients who neither relapse nor die by the data cutoff date will be censored at the last follow up date.
- Distant metastasis free survival (DMFS), defined as the duration of time from the date of positive ctDNA being confirmed to the date of appearance of a distant metastasis or death, whichever occurs first. Patients who neither develop distant metastasis nor die by the data cutoff date will be censored at the last follow up date.
- Overall survival (OS), defined as the duration of time from the date of positive ctDNA being confirmed to death from any cause. Patients who are alive by the data cutoff date will be censored at the last follow up date.

- Safety and tolerability will be defined as the number of treatment (i.e., atezolizumab and tiragolumab) related grade 3 or greater adverse events (AEs). Adverse events will be assessed using CTCAE v5.0 criteria. Safety will be monitored from the time of initiation of study treatment to 30 days after discontinuation of therapy.

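### A non-Stage-0 new primary melanoma found on treatment can end follow-up and censor a patient who has had no RFS event under Section 11, because Section 6.2.1 labels it disease recurrence

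*Combined protocol and SAP*

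**What the plan says.** Section 11 defines an RFS event as "recurrence of melanoma at any site (local, in-transit or regional lymph nodes or distant recurrence) or death due to any cause". It then adds: "New incident cases of melanoma and second cancer diagnoses are not counted as events for recurrence-free survival". That exclusion makes no distinction between in situ and invasive new melanomas.

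Section 6.2.1 lists the reasons for stopping study treatment. One of them is "Disease recurrence (local, regional, or distant), including new primary melanoma (except MMIS Stage 0". Patients with the excepted Stage 0 lesion may continue treatment at the investigator's discretion.

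Section 5.6 says that "patients who stop treatment due to recurrence will be considered off study and will no longer be followed after the 90-day follow-up" for adverse events. Section 5.7 promises three years of follow-up from surgery "unless treatment is discontinued due to disease recurrence, in which case the patient will be considered off study" after the same 90-day period.

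Section 14.3 runs RFS "to the date of earliest disease relapse or death, whichever occurs first" and adds: "Patients who neither relapse nor die by the data cutoff date will be censored at the last follow up date". Neither Section 14.3 nor the endpoint table in Section 2.0 defines relapse, mentions new primaries or refers to Section 11. In Section 10.0 the Recurrence Form is due at "Time of disease recurrence", again without a definition.

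**The concern.** The label in Section 6.2.1 and the endpoint rule in Section 11 do not fit together, and the follow-up rules in Sections 5.6 and 5.7 act on the label. A site whose patient develops an invasive new primary during treatment has a protocol section that calls this disease recurrence. If it carries that label into Sections 5.6 and 5.7, scheduled disease assessment ends. The analyst applying Section 11 then has a patient with no RFS event, and not necessarily a DMFS event, whose follow-up stopped for a melanoma-related reason.

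Kaplan-Meier estimation assumes that patients censored at a given time have the same outlook as those still followed. That is doubtful when the trigger is another melanoma. Correct coding at analysis cannot recover assessments that were never made. RFS, DMFS and OS are all stated secondary endpoints. They are also the outcomes for the ctDNA-kinetics objective, and Section 14.7 plans a log-rank test on them.

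**Working it through.** The plan gives no event count, hazard ratio or power for RFS, so there is no stated figure to reproduce. The check has two parts.

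**1. One patient followed through the text.** Take a new primary that is not MMIS Stage 0, found during treatment.

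- Section 6.2.1: treatment stops, under the label disease recurrence.
- Sections 5.6 and 5.7: a stop for recurrence means off study after 90 days.
- Section 11: no RFS event.
- Section 14.3: no relapse or death recorded, so censored at last follow-up. DMFS and OS are censored in the same way if there is no distant metastasis or death.

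No section reconciles these steps. The route is limited to the treatment period (up to 13 cycles of 28 days, 364 days). A new primary found after treatment has ended raises only the question of what relapse means in Section 14.3.

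**2. Size, as an illustration.** From the plan: arm sizes of 18 (reference) and 43 (combination, if stage 2 opens), and the 90-day period, taken as 3 months. Assumed, because the documents give no figures: new primary at month 9; true relapses or deaths of 7 of 18 and 17 of 43 by month 36 (about 39%), evenly spaced; no other censoring.

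For the 18-patient arm the true events fall every 36/8 = 4.5 months, so two have occurred by month 12.

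With one new primary:
- Counted as an event: (18 − 8)/18 = 10/18 = 55.6%.
- Censored at month 12: 16/18 up to that point; the risk set then falls from 16 to 15 and five more events follow, so 16/18 × 10/15 = 59.3%.
- Non-event, still followed: 11/18 = 61.1%.

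With three new primaries:
- Event: 8/18 = 44.4%.
- Censored: 16/18 × 8/13 = 54.7%.
- Followed: 61.1%.

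For the 43-patient arm the true events fall every 36/18 = 2 months. With one new primary:
- Event: 25/43 = 58.1%.
- Censored at month 12, with the true event due that month placed just after it: 38/43 × 25/37 = 59.7%.
- Followed: 26/43 = 60.5%.

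For one patient, event versus censored therefore differs by 59.3 − 55.6 = 3.7 points in the 18-patient arm and 59.7 − 58.1 = 1.6 points in the 43-patient arm. Event versus followed non-event differs by 1/18 = 5.6 and 1/43 = 2.3 points. The loss caused by ending follow-up when Section 11 is applied correctly is the gap between censored and followed: 61.1 − 59.3 = 1.8 and 60.5 − 59.7 = 0.8 points. In this illustration the new-primary patient has no later relapse; if that patient would have relapsed, the error would run the other way.

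**The case against.** A reader might infer that two sections code the same event in opposite ways for RFS. The documents do not support that. Only Section 11 codes new primaries for RFS, and it is explicit. Section 6.2.1 is a treatment-stopping list and defines no endpoint. Section 14.3 is silent on what relapse means, which is a gap and not a contradiction. Counting a new primary as an RFS event would require setting aside a specific rule in favour of a label borrowed from a stopping criterion.

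A reader might also infer that the Recurrence Form would record a new primary as a recurrence. Only the form's name and timing are in the documents. Its fields are not, and they may already separate the two.

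The off-study step is itself a reading. Sections 5.6 and 5.7 do not mention new primaries, and the stopping list in Section 5.6 speaks of confirmed progression. A site reaches off study by carrying the Section 6.2.1 label across. The documents make that natural, but they do not make it certain.

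Finally, RFS is secondary, Section 14.7 calls all analyses exploratory, and Section 14.1 rules out a formal efficacy comparison with the reference arm.

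All of this stands and limits the point. It does not remove it. Even if Section 11 governs the coding without dispute, the label still leads to the off-study rule, and follow-up can end for a patient with no event.

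**Conclusion.** The point holds in this form: a non-Stage-0 new primary found on treatment can take a patient off study and censor RFS, DMFS and OS without an RFS event under Section 11, possibly informatively, while relapse in Section 14.3 is left undefined.

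The frequency is unknown because the documents give no new-primary rate; it is probably a few patients at most. Under the assumed inputs above, one such patient shifts 3-year RFS by about 2 to 6 points in the 18-patient arm and about 1 to 2 points in the 43-patient arm, depending on which two treatments of the patient are compared. That the censoring is informative is plausible but cannot be shown from the documents.

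The C3D1 ctDNA clearance endpoint and the Simon decision rule (3 of 18, then 8 of 43) do not use RFS and are untouched. This is worth correcting because the stated rules conflict and lost follow-up cannot be recovered. It does not threaten the trial's main conclusion.

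**What to change.** 1. In Sections 2.0 and 14.3, state that RFS uses the Section 11 event definition.
2. In Section 6.2.1, reconcile the recurrence wording with Section 11 so that a new primary melanoma is identified separately from recurrence. Whether a new primary stops treatment is for the sponsor to decide and is not judged here.
3. Reconcile Sections 5.6 and 5.7 so that the off-study exception, as it applies to endpoint follow-up, rests on the same definition of recurrence as the RFS event.
4. Confirm that the data collected distinguish recurrence from new primary; if the case report form already does so, nothing needs adding.

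The cost is wording in five sections, a check of one form, and continued scheduled follow-up for the few patients concerned.

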12.0 DATA AND SAFETY MONITORING

In compliance with the Washington University Institutional Data and Safety Monitoring Plan, an independent Data and Safety Monitoring Board (DSMB) will be specifically convened for this trial to review toxicity data. A DSMB will consist of no fewer than 3 members including 2 clinical investigators and a biostatistician. DSMB members must be employed by Washington University, Barnes-Jewish Hospital, or St. Louis Children's Hospital. Like investigators, DSMB members are subject to the Washington University School of Medicine policies regarding standards of conduct. Individuals invited to serve on the DSMB will disclose any potential conflicts of interest to the trial principal investigator and/or appropriate university officials, in accordance with institution policies. Potential conflicts that develop during a trial or a member's tenure on a DSMB must also be disclosed.

Until such a time as the first secondary site enrolls its first patient, a semi-annual DSM report to be prepared by the study team will be submitted to the Quality Assurance and Safety Monitoring Committee (QASMC) semi-annually beginning six months after study activation at Washington University (if at least one patient has been enrolled) or one year after study activation (if no patients have been enrolled at the six-month mark).

The DSM report for the DSMB will be prepared by the study team with assistance from the study statistician, will be reviewed by the DSMB, and will be submitted to the QASM Committee. The DSMB must meet at least every six months beginning six months after enrollment of the first patient at a secondary site, no more than one month prior to the due date of the DSM report to QASMC. This report will include:

- HRPO protocol number, protocol title, Principal Investigator name, data coordinator name, regulatory coordinator name, and statistician
- Date of initial HRPO approval, date of most recent consent HRPO approval/revision, date of HRPO expiration, date of most recent QA audit, study status, and phase of study
- History of study including summary of substantive amendments; summary of accrual suspensions including start/stop dates and reason; and summary of protocol exceptions, error, or breach of confidentiality including start/stop dates and reason
- Study-wide target accrual and study-wide actual accrual including numbers from participating sites
- Protocol activation date at each participating site
- Average rate of accrual observed in year 1, year 2, and subsequent years at each participating site
- Expected accrual end date, accrual by site, and accrual by cohort
- Objectives of protocol with supporting data and list the number of participants who have met each objective
- Measures of efficacy

- Early stopping rules with supporting data and list the number of participants who have met the early stopping rules
- Summary of toxicities at all participating sites and separated by cohorts
- Abstract submissions/publications
- Summary of any recent literature that may affect the safety or ethics of the study

Further DSMB responsibilities are described in the DSMB charter.

The study principal investigator and coordinator will monitor for serious toxicities on an ongoing basis. Once the principal investigator or coordinator becomes aware of an adverse event, the AE will be reported to the HRPO and QASMC according to institutional guidelines (please refer to Section 7.0).

Refer to the Washington University Quality Assurance and Data Safety Monitoring Committee Policies and Procedures for full details on the responsibilities of the DSMB. This is located on the QASMC website at <https://siteman.wustl.edu/research/clinical-research-resources/protocol-office-prmcqasmc/>.

13.0 AUDITING

As coordinating center of this trial, Washington University (via the Quality Assurance and Safety Monitoring Committee (QASMC)) will monitor each participating site to ensure that all protocol requirements are being met; that applicable federal regulations are being followed; and that best practices for patient safety and data collection are being followed per protocol. Participating sites will be asked to send copies of all audit materials, including source documentation. The audit notification will be sent to the Washington University Research Patient Coordinator, who will obtain the audit materials from the participating institution.

Notification of an upcoming audit will be sent to the research team one month ahead of the audit. Once accrual numbers are confirmed, and approximately 30 days prior to the audit, a list of the cases selected for review (up to 10 for each site) will be sent to the research team. However, if during the audit the need arises to review cases not initially selected, the research team will be asked to provide the additional charts within two working days.

Items to be evaluated include:

- Subject screening and enrollment
- Reporting of adverse events
- Maintenance of HIPAA compliance
- Completeness of regulatory documentation
- Completeness of participant documentation
- Acquisition of informed consent
- IRB documentation
- Issues of protocol adherence

Additional details regarding the auditing policies and procedures can be found at <https://siteman.wustl.edu/research/clinical-research-resources/protocol-office-prmcqasmc/>.

14.0 STATISTICAL CONSIDERATIONS

14.1 Study Design

This is an open-label, multi-center, Simon two-stage phase II study consisting of random allocation of a portion of patients to a small reference arm to offer some protection against the uncertainties and potential biases of a one-armed study while retaining some of the statistical efficiency. The reference arm is not a control group in the traditional sense and there will not be a formal efficacy comparison between the treatment and reference groups (Herson and Carter, 1986; Rubinstein, et. al., 2009).

The purpose of this study is to evaluate the efficacy and safety of atezolizumab and tiragolumab in stage II melanoma patients who had undergone complete resection and been tested positive for circulating tumor DNA (ctDNA). In this study, the treatment arm (i.e., atezolizumab and tiragolumab) will not be compared with the reference arm (i.e., atezolizumab only); it will be analyzed against historical control as a one-armed study. The reference arm is intended to only act as a check on the similarity of the current patients to the historical control for a descriptive estimation of ctDNA clearance.

14.2 Primary Endpoint

ctDNA clearance rate, defined as the proportion of ctDNA+ patients having a ctDNA negative test at C3D1.

14.3 Secondary Endpoints

- Confirmed ctDNA negative rate, defined as the proportion of ctDNA-positive patients having two consecutive negative ctDNA tests.
- Relapse free survival (RFS), defined as the duration of time from the date of positive ctDNA being confirmed to the date of earliest disease relapse or death, whichever occurs first. Patients who neither relapse nor die by the data cutoff date will be censored at the last follow up date.
- Distant metastasis free survival (DMFS), defined as the duration of time from the date of positive ctDNA being confirmed to the date of appearance of a distant metastasis or death, whichever occurs first. Patients who neither develop distant metastasis nor die by the data cutoff date will be censored at the last follow up date.
- Overall survival (OS), defined as the duration of time from the date of positive ctDNA being confirmed to death from any cause. Patients who are alive by the data cutoff date will be censored at the last follow up date.

- Safety and tolerability will be defined as the number of treatment (i.e., atezolizumab and tiragolumab) related grade 3 or greater adverse events (AEs). Adverse events will be assessed using CTCAE v5.0 criteria. Safety will be monitored from the time of initiation of study treatment to 30 days after discontinuation of therapy.

